Achieving a comfortable and functional connection between an amputee and their prosthetic limb is critical to the success of the prosthesis. Therefore, the socket system is the most significant component for overall success of the prosthesis^{1,2}. In an effort to maximize socket performance and comfort without adversely affecting residual limb health, a prosthetist custom fits a socket for every patient using plaster wraps or computer aided design. Currently, this process suffers from a lack of quantitative feedback to determine appropriate socket fit. Prosthetists aim to minimize suspension-dependent movement between the socket and residual limb, but current approaches are limited as they rely on anecdotal visual cues along with subjective verbal feedback from the patient. Prosthetists then use this information to revise socket parameters such as volume, geometry, and type of suspension to provide current 'best' fit for a patient. Regardless of prosthetist fitting, the volume of mature residual limb (>18 months post-amputation³) are subject to daily⁴ and chronic^{5,6} changes in volume that compromise socket fit and performance. For the 1 million Americans that live with a lower-limb amputation, a growing number of which are service men and women⁷⁻⁹, these volume changes adversely affect fit, performance, and residual limb health⁶ – including skin breakdown and ulceration¹⁰ that can necessitate revision of the amputation. Indeed, for traumatic lower-limb amputations, the requirement for surgical revision is known to be as high as 30%¹¹.

II. Objective:

Aim 1 will evaluate the relationship between vacuum pressure and limb movement inside the socket and how it changes with respect to vacuum pressure setting, gait speed and socket volume

Aim 2 will evaluate the impact of socket movement on residual limb circulation and residual limb skin health

Aim 3 will compare the effectiveness of an adaptive vacuum system to standard of care suspension prosthetics (pin-locking or suction).

Study Population: Up to 170 amputees will be enrolled in the study overall.

1. **Aim 1:** 10 trans-femoral amputees and 10 trans-tibial amputees will be enrolled.
2. **Aim 2:** 15 trans-tibial and 15 trans-femoral amputees will be enrolled.
3. **Aim 3:** n=120 (trans-tibial and trans-femoral amputees) will be enrolled.

III. Inclusion Criteria:

1. Ages of 18 and above

2. Unilateral trans-tibial or trans-femoral amputee
3. Ambulate at a K2 level or higher

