4. At least 3 months post-amputation per physician discretion
5. Residual limb length greater than 6.5 inches in length
6. Able to follow directions and give informed consent on their own or through Legally Authorized Representative.
7. Must be able to ambulate without assistance. An external assistance device such as cane or walker will be permitted.
8. Adequate arterial blood flow of the index stump as evidenced by TcOM > 30 mmHG, measured within the past 12 months.

IV. Exclusion Criteria:

1. Conditions that prevent wearing a prosthetic socket; such as existing scab, ulcer, or keloid scar on amputation stump.
2. Cognitive deficits or mental health problems that would limit ability to consent and participate fully in the study protocol
3. Women who are pregnant or who plan to become pregnant in the near future

V. Study Design:

This study has 3 aims where trans-femoral and trans-tibial amputees will be enrolled.

Subjects enrolled in Aim 1 (N=20) will have one study visit that will take place at The Ohio Willow Wood (OWW).

Subjects enrolled in Aim 2 (N=30) will have a total of 4 visits at baseline, month 1, month 2, and month 3.

Subjects in Aim 3 (120) will be enrolled at Indiana University (n=30 subjects), OWW (n=30), and at Walter Reed National Military Medical Center (WRNMMC) (n=60 subjects) with a total of 3 visits at 0 week (baseline), 0-4 weeks (socket fitting visits), and 16 weeks (final visit).. OWW and Walter Reed National Military Medical Center (WRNMMC) have separate IRB protocol & approval to conduct their part of subject recruitment and study visits. Aims 2 and 3 will not be run concurrently. Subjects enrolled in Aim 2 can participate in Aim 3. Aim 2 studies performed at Ohio State and Indiana University. Aim 2 has enrolled 15 subjects through Ohio State University & OWW (and these 20 subjects have completed their participation in the study) and the data is currently being analyzed to determine if additional subjects are required. If analysis shows sufficient subjects have been enrolled to achieve the study aim, no additional subjects will be enrolled in Aim 2. If there is insufficient data, the remainder of the Aim 2 subjects will be enrolled through OWW under their approved IRB with WIRB. Aim 3 studies performed at IU, OWW and WRNMMC per their approved IRB protocols. The vacuum suspension used for the study is new to all enrolled subjects

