On this day, prior to socket fitting activities, the arterial blood flow will be measured on the index stump if not already completed per standard of care within the previous 12 months prior to enrollment for data analysis. Those with an TcOM < 30 mmHG be excluded and no further study activities will be completed. These subjects will be recorded as a screen fail and will not be enrolled.

Others will move forward with socket fitting activities.

- A. **Study Visit #1 - Socket Fitting visits (Week 0 - 4, +/- 2 weeks) – Note: this visit may consist of three (minimum) visits plus socket adjustment visits (as needed by the subject) on separate days (up to 4 weeks)**
 - i) limb shape capture, measurements or tracing
 - ii) diagnostic static fitting and diagnostic dynamic fitting
 - iii) delivery of definitive “research” socket

Once delivery of the definitive research socket has been completed, the subject will be allowed to return for no greater than 4 adjustments (within 0-2 weeks from baseline) to obtain a comfortable fit in order to complete this study. If subject requires more than 4 adjustment visits, the participation from the study will end.

Once the subject is comfortable with the fitting, the date will be noted by the study team as **“research socket use start date”**. From this date, the subject will begin wearing the test socket for next 16 weeks.

- B. **Study Visit #2A - Baseline visit for residual limb health (Week 4, +/- 2 weeks)** Enrollment, after delivery of the definitive research socket and completion of the socket fitting visits, the following research activities will take place to obtain baseline measurements:

- Subjects will be asked to walk on a treadmill for 10 mins. The residual and sound (intact) limb health measurements will be taken before and after the activity period with the exception of conducting post-activity ultrasound and digital imaging. The purpose of acquiring ultrasound and digital imaging is to determine changes in skin structure on a long-term basis; thus, these measurements will only be collected during pre-activity procedures to observe changes in a resting state. The following health measurements will take place:
 - Surface Electrical Capacitance
 - TEWL measurement
 - Hyperspectral Imaging
 - Ultrasound (pre-activity only)
 - Perfusion/ Blood flow
 - Digital Image (pre-activity only)

B.i. Study Visit #2B - Baseline visit for gait assessment (Week 4, +/- 2 weeks)**

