***Note* Study Visit #2A and #2B can be combined and performed in a single study visit upon the discretion of the subject.**

Subjects will begin in their current standard of care prosthesis (the prosthesis worn at time of study enrollment), wherein the following research activities will take place in the following order:

- Subjective questionnaires [Veterans RAND 36-Item Health Survey (VR
- 36, PEQ, Socket Comfort Scores (SCS), and National Institute of Health (NIH) Patient-Reported
- Outcomes Measurement Information System (PROMIS)
- Functional evaluation [Comprehensive High-level Activity Mobility Predictor (CHAMP)]
- Biomechanical evaluation of gait during 6min walking test
 - a. Positioning markers will be placed on the subject while performing the walking assessment to track and describe the movement of the body in three dimensions.
- Repeat SCS outcome

**** applicable to any new enrollments and/or any already enrolled subject completed their limb health part (16 weeks in test sockets followed by 4 weeks in SoC socket as wash off period)**

Following completion of these activities in study visit 2A & B, the subjects will be fitted with the adaptive vacuum suspension by a certified prosthetist that they will wear subsequently wear the device for 16 weeks

The study team will follow up subjects with a weekly phone call to determine the compliance for the use of research socket.

C. **Study Visit #3A – Final Visit (Week 16, +/-2 weeks).** After 16 weeks of wearing the “research” socket the following research activities will take place in the following order:

- Subjects will be asked to walk on a treadmill for 10 mins. The following residual and sound limb health measurements will be taken before and after the activity period with the exception of conducting post-activity ultrasound and digital imaging, is as follows
 - Surface Electrical Capacitance
 - TEWL measurement
 - Hyperspectral Imaging
 - Ultrasound (pre-activity only)
 - Perfusion/ Blood flow
 - Digital Image (pre-activity only)

C.i **Study Visit #3B**— the visit will take place either the same day of Visit 3A or another day within the Week 16, +/-2 weeks based on subject convenience, to repeat research activities previously performed in study visit # 2A

- Subjective questionnaires [Veterans RAND 36-Item Health Survey (VR 36, PEQ, Socket Comfort Scores (SCS), and National Institute of Health (NIH) Patient-Reported Outcomes Measurement Information System (PROMIS)]

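### In the IU Aim 3 functional, gait and questionnaire comparison, a newly made and adjusted socket is set against the existing prosthesis, so new-socket fit cannot be separated from suspension type

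*Combined protocol and SAP*

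**What the plan says.** **Aim.** Section II says that Aim 3 will "compare the effectiveness of an adaptive vacuum system to standard of care suspension prosthetics (pin-locking or suction").

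**Test condition.** Section VIII, Visit #1, starts with capture of the limb shape and diagnostic static and dynamic fitting, and ends with "delivery of definitive “research” socket". After that, "the subject will be allowed to return for no greater than 4 adjustments" so that a comfortable fit is reached. A subject who needs more than four leaves the study.

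**Comparator.** At Visit #2B the questionnaires, Socket Comfort Score, CHAMP and gait analysis are done in "the prosthesis worn at time of study enrollment". No remake, refit, fit check or limit on socket age is stated before these measurements. The study prosthetist's review and adjustment of the standard prosthesis is listed after the Visit #3B assessments.

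**Analysis.** Section XV fits a random-effects model with terms for group (EVS versus suction, or EVS versus pin-locking/lanyard), sequence and visit. Age, diabetes and smoking are covariates. Section IX.B says that CHAMP will show the effect of the socket suspension intervention.

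**Sites.** Aim 3 plans 120 subjects: 30 at IU, 30 at OWW and 60 at WRNMMC. The last two "have separate IRB protocol & approval to conduct their part of subject recruitment and study visits". The visits described here are IU's.

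**The concern.** Two things change together between Visits 2B and 3B: the suspension, and the socket, which is new, individually fitted and recently adjusted. The protocol's own background gives the reason to care. It names the socket system as the component that matters most for success, and says that changes in limb volume spoil fit and performance. Several outcomes respond directly to fit: the Socket Comfort Score asks about nothing else, and the PEQ has a residual limb health scale.

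If the result is reported as a suspension effect, a benefit that any newly made socket would have given could be credited to the vacuum system. A larger sample does not help, because this is bias and not imprecision.

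**Working it through.** The plan gives no effect size, SD or power for Aim 3, so it has no figure to reproduce. Only the site total can be checked: 30 + 30 + 60 = 120.

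**1. Can the two effects be separated?** Code each measurement by intercept, EVS (0/1) and new socket (0/1).

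| Design | Distinct rows | Rank / columns |
|---|---|---|
| IU visits as described: own standard, then new EVS | (1,0,0), (1,1,1) | 2 of 3 |
| Two-sequence crossover as in Section XV, with visit and sequence added | four sequence-by-visit cells | 4 of 5 |
| With a third condition: newly made socket on standard suspension | (1,0,0), (1,0,1), (1,1,1) | 3 of 3 |

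In the first two designs the new-socket column equals the EVS column, so only the sum of the two effects can be estimated. Making the study a true crossover would not remove this. Age, diabetes and smoking are subject-level covariates and cannot separate two conditions within a subject.

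The footnote to Visit #2B also admits subjects who have already completed 16 weeks in the test socket and 4 weeks back in standard of care. For them the order differs, but the study-made socket still goes with EVS and the subject's own socket with standard of care.

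**2. What could a new-socket effect do to the test?** This is an illustration, because the documents give no size. Assume that the suspension effect is zero and that a new socket shifts the mean within-subject difference by d SDs *of that difference*. For a two-sided 0.05 paired t-test,

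P(significant) = P(T > c) + P(T < −c),

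where T is noncentral t with n − 1 df and noncentrality d√n, and c is the 0.975 quantile of central t with n − 1 df.

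| d (assumed) | n = 30: d√n | significant (c = 2.045) | n = 60: d√n | significant (c = 2.001) |
|---|---|---|---|---|
| 0.15 | 0.822 | 12.5% | 1.162 | 20.8% |
| 0.20 | 1.095 | 18.5% | 1.549 | 33.2% |
| 0.30 | 1.643 | 35.5% | 2.324 | 62.8% |

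n = 30 is IU's full Aim 3 allocation. The rationale in Section VIII extends functional testing to the remaining enrolments, so the actual number may differ. n = 60 would require another 30 subjects measured in the same way.

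**3. Sensitivity of these figures.**
- *Holm.* If the first step were tested at 0.025 (two hypotheses), the n = 60 figures fall to 14%, 23% and 51%. At n = 30, c = 2.364 gives 7%, 12% and 25%. Section XV does not say how many hypotheses are in the family.
- *Scale.* If d is in SDs of the outcome itself, divide it by √(2(1 − ρ)), where ρ is the within-subject correlation. At ρ = 0.5 nothing changes. At n = 60, ρ = 0.2 gives 15%, 23% and 44%, and ρ = 0.8 gives 44%, 67% and 95%.

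**The case against.** **A whole-system comparison is legitimate.** Section II speaks of an adaptive vacuum system, and Section V describes the device as a socket system. New system versus usual prosthesis is a fair pragmatic question. This stands, and it is why the main remedy concerns the wording of the claim. It does not support the suspension label in Sections IX.B and XV.

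**The direction is not fixed.** A reader might infer that the comparison must favour the test system. The documents do not establish that. The research socket is itself exposed to volume change: its adjustments fall in the first weeks, and it is assessed after 16. The vacuum suspension is new to every subject, so familiarity may favour the old prosthesis. Excluding subjects with an existing scab or ulcer may also remove some of the worst-fitting standard sockets. On the other side, subjects whose test socket needs more than four adjustments leave the study, and the standard socket has no matching rule. Bias towards the test system is plausible but unproven.

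**The scope is limited.** A reader might extend the point to all of Aim 3. The documents do not support that either. The stated comparator belongs to Visit 2B. For limb health at Visit 2A the prosthesis worn is not stated: Visit #2A is placed after delivery of the research socket, while the text after Visit #2B has the adaptive vacuum fitted after both. The OWW and WRNMMC protocols may handle the standard socket differently.

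**Socket age is a weak remedy.** It varies between subjects, and a recently made standard socket has still not been through the study's fitting and adjustments. This stands, so the analysis can only be supportive.

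**Conclusion.** The concern holds for the functional, gait and patient-reported outcomes in the IU Aim 3 visits, 2B versus 3B. There, new-socket fit and suspension type are completely aliased, and neither the planned model nor a crossover sequence can separate them. This rests on reading Visit #3B as measured in the research socket, which its timing implies, and on the absence of any stated refit of the standard prosthesis before Visit #2B.

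The size is unknown. The illustrative 12.5% to 35.5% at n = 30 (20.8% to 62.8% at n = 60) depends on assumed shifts in SDs of the within-subject difference, no suspension effect and no Holm adjustment. IU can still answer whether a newly fitted adaptive-vacuum prosthesis does better than the one already worn. It cannot say that the suspension is the reason. The point is neither shown nor excluded for limb health, OWW and WRNMMC.

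**What to change.** 1. **Conclusion.** In Sections II, IX.B and XV, describe the Aim 3 contrast as a newly fitted adaptive-vacuum prosthesis versus the existing prosthesis, not as an effect of suspension alone. Make this unconditional: agreement in a sensitivity analysis should not restore the suspension claim.
2. **Data.** Record at enrolment the date the standard socket was made and the date it was last adjusted. Obtain both retrospectively, where possible, for subjects already enrolled.
3. **Analysis.** Add standard-socket age (continuous) and its interaction with device as a supportive sensitivity analysis. Report the device effect at low socket age with its confidence interval, and state that this does not remove the aliasing.
4. **Text.** Reconcile the Visit #2A and #2B passages on which prosthesis is worn for the limb-health baseline, and check whether the OWW and WRNMMC protocols describe the same comparison.

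The cost is two data fields, one additional model and some rewording, with no new sockets or visits. The downside is a narrower claim and an imprecise sensitivity estimate. Only a condition with a newly made, equally adjusted socket on the standard suspension would separate the two effects. That is a much larger change, and it is not needed for the narrower claim.

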- Hitachi Aloka Ultrasound – A hand held device will be moved gently across the skin and measure your blood flow of deeper skin tissues.
- Skin Temperature-A small tab (small sticker) will be placed on the skin and tell us the temperature of your residual limb
- Surface Electrical Capacitance – Small non-invasive probe place on skin to measure skin hydration
- Trans epidermal water loss measurement (TEWL) – Small non-invasive probe compares relative humidity of skin surface to indicate epidermal barrier function
- Transcutaneous Oxygen Measurement – Small non-invasive probe measures the amount of oxygen released through the skin layer
- This data will be used to determine how socket movement affects the limb health measurements
- The study prosthetist will set vacuum level set to first level
- Digital Image

2. Study Visit 2, 3, 4 (month 1, 2, 3) Subjects will return at 1, 2, and 3 months after study visit 1 where the following research activities will take place:

- Subject will perform seated tasks, standing tasks, and walking on a treadmill task. Skin health measurements will be taken before and after the activity period.
- Hyperspectral Imaging
- Hitachi Aloka Ultrasound
- Skin Temperature
- Surface Electrical Capacitance
- TEWL measurement
- Transcutaneous Oxygen Measurement
- This data will be used to determine how socket movement affects the limb health measurements
- The study prosthetist will set the vacuum level set to the next treatment level except at study visit 4.
- At the end of visit 4, patients will be returned to their standard of care prosthesis. The study prosthetist will be available to review and adjust the fit of their existing prosthesis.
- Digital Image

VIII. Aim 3 (n=30 will be performed at IU under current approved protocol):

Rationale for the amendment: As per the approved DoD proposal, n=60 (n=30 each at IU and Willow wood for Limb Heath analysis, current approved IU IRB protocol) and n=60 subjects were supposed to be completed at Walter Reed (WR) for Functional analysis. We have received a request from WR to perform Functional analysis on the remaining subject that will be enrolled for limb health analysis (this is due to COVID-19 and availability of subjects at WR. The request from WR was also in view of short time line remaining (study end date 09/2021).

After receiving consent, the first enrollment visit will be scheduled for the subjects to see the IU study prosthetist to initiate the “test” socket fitting visits.

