- A. Demographic, medical, and subjective questionnaires: Subjects will be queried on self-reported measures of user comfort and performance. Briefly, four subjective measures will be completed: VR-36, PEQ, SCS, and measures from the NIH PROMIS. The VR-36 was developed from the original RAND version of the Medical Outcomes Study 36-Item Health Survey as a short form functional assessment for veterans. The PEQ is composed of 9 validated scales to measure various aspects of a prosthesis and the users feelings about it. The scales include: Ambulation, Appearance, Frustration, Perceived Response, Residual Limb Health, Social Burden, Sounds, Utility, and Well Being. The SCS is based on a 0-10 numerical scale that assesses comfort rather than pain. The SCS will be administered by asking the participant: "If 0 represents the most uncomfortable socket fit you can imagine and 10 represents the most comfortable socket fit, how would you score the comfort of the socket fit of your artificial limb at the moment?". The NIH developed a system of reliable, precise measures to be used to capture patient-reported physical, mental, and social well-being. The PROMIS tools are aimed at helping clinical researchers most appropriately quantify how a patient is feeling or what they are able to do.

- B. Comprehensive High-level Activity Mobility Predictor (CHAMP) Test: The CHAMP test will be used to assess overall amputee performance and the effect of the socket suspension intervention over time. The conglomeration of clinical assessment tools into the CHAMP was specifically done to measure high-level mobility in service members with a lower limb amputation. CHAMP consists of the Single Leg Stance Test (SLS), the Edgren Side Step Test (ESST), Illinois Agility Test (IAT), and T Test. The SLS measures the time an amputee is able to stand in single support with their hands on their hips and is performed with eyes open and with eyes closed. The ESST measures the ability of the participant to side shuffle back and forth in the layout shown in Figure 20 for 10 seconds. A point is given for each cone passed which is totaled for the 10 seconds. The IAT and T-test requires additional agility and control to navigate the course. Participants will complete the tasks in the following order: SLS, ESST, T-Test, and IAT. To generate a composite CHAMP score, the best times or point for each task is converted to a 0-10 scale following the scoring system. The

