composite CHAMP score will range from 0-40, with 40 representing the highest level of performance.

- C. Biomechanical evaluation of gait: IU Neuroscience Gait lab will be used to collect kinematic data. The laboratory is equipped with an instrumented treadmill and infrared camera system. A harness system will be used to provide support and safety for the amputees while study participants walk on the treadmill for 6 minutes. A specially designed reflective marker set, will track movement between the socket and residual limb and allow analysis of motion not detected by the vacuum system, to quantify and characterize soft-tissue specific pistonning across suspension platforms. Reflective passive markers will be placed on the amputee and prosthesis, including the socket. A virtual marker position will be created for the residual limb from the physical markers. A series of segment definitions will be based off the reflective marker positions. The 3-dimensional position and orientation of a segment will be tracked relative to the segment immediately proximal using transformation matrices.
- D. Transcutaneous Oxygen Measurement and skin temperature:
The PeriFlux System 5000 uses non-invasive probes that will measure the skin temperature and transcutaneous Oxygen Measurement. The probe head is affixed to the residual limb by an adhesive sticker.
- E. Hyperspectral Imaging for tissue oxygenation and perfusion:
Powered by spatial frequency domain imaging, this imaging system provides a more complete picture of tissue health by quantifying and mapping tissue oxygenation and perfusion. Data are displayed in the form of color-coded maps.

X. Potential Risks:

There may be risks that are not known about at this time. Side effects, risks, and discomforts may result from study participation.

Prosthesis placement: While the goal of this project is to create a more comfortable prosthesis, it is possible that the subject could experience discomforts commonly associated with prosthesis use, such as perspiration, dry skin, rash, itching, blisters, high pressure in the socket, looseness in the socket, and mechanical rubbing that leads to ulceration which may lead to infection and additional surgery. Subjects with low levels of arterial blood flow have an additional risk of ulceration.

Treadmill task:

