There is a risk of falling during the research activities. This risk is mitigated by the ability of participants to self-select pace for the treadmill task and observation of treadmill activities by research staff.

Transcutaneous Oxygen Measurement and skin temperature:

The PeriFlux System 5000 poses minimal risk to the subject. Removal of the sticker after data acquisition may cause minor discomfort similar to removing a small band-aid.

Hyperspectral Imaging for tissue oxygenation and perfusion:

This non-invasive non-contact imaging technique poses minimal risk to the subject.

Ultrasound:

Ultrasound imaging is a noninvasive technique and is a minimal risk procedure.

TEWL and Surface Electrical Capacitance Measurements:

TEWL and Surface Electrical Capacitance measurements are noninvasive and propose less than minimal risk.

Loss of Confidentiality

Although efforts are made to protect your study records, there is always a risk that someone could get access to your private health records.

XI. Unanticipated Problems and Adverse Event Reporting

Protocol deviations and Unanticipated Problems Involving Risks to Subjects or Others, Adverse Events, and Other Problems will be reported to the Indiana University per IU IRB reporting requirements.

Unanticipated problems can occur in any type of research (medical or non-medical) and may include occurrences such as adverse events, subject complaints, protocol deviations, and other untoward events involving risk. Events requiring prompt reporting by investigators and research staff may involve physical, psychological, social, legal, or economic harms.

Event reports and accompanying information will be screened for completeness by research staff members, additional clarifications will be requested from the investigator as necessary. Research staff members and the principal investigator will make an initial determination about whether the event represents a possible unanticipated problem involving risks to subjects or others and/or potential noncompliance. Reports of events determined during screening to represent possible unanticipated problems involving risks to subjects or others and/or serious/continuing noncompliance will be forwarded to the IRB for convened review. Reports of events that do not meet the requirements for prompt reporting may be reported at time of study renewal.

XII. Discontinuation Criteria

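### Aim 3 at Indiana University plans no active skin question or event record between the early adjustment visits and the final visit; the weekly call is stated to cover compliance only

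*Combined protocol and SAP*

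**What the plan says.** Section VIII describes Aim 3 at Indiana University (IU) for 30 subjects. Section V states that OWW and WRNMMC run their parts under separate IRB protocols.

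- **Early contact.** After delivery of the definitive socket, "the subject will be allowed to return for no greater than 4 adjustments (within 0-2 weeks from baseline") to reach a comfortable fit. These visits are as needed.
- **Baseline and final visits.** Visit 2A/2B is at Week 4 and Visit 3A/3B at Week 16, each with a window of two weeks. Limb measurements and a digital image are taken at 2A and 3A. Questionnaires are given at 2B and 3B.
- **Between them.** "The study team will follow up subjects with a weekly phone call to determine the compliance for the use of research socket". No other purpose is given for the call.
- **Expected harms.** Section X lists "perspiration, dry skin, rash, itching, blisters" among the possible discomforts, and also "mechanical rubbing that leads to ulceration which may lead to infection and additional surgery".
- **Event handling.** Section XI sends adverse events, complaints and other problems to the university under its IRB requirements. It adds: "Reports of events that do not meet the requirements for prompt reporting may be reported at time of study renewal".
- **Analysis.** Section XV plans models for CHAMP performance and residual limb health. It plans no summary of skin events.

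**The concern.** The background section motivates the device by skin breakdown and ulceration, and section IV excludes anyone with an existing scab or ulcer on the stump. Yet once the subject is wearing the test socket, nobody is scheduled to ask whether such a lesion has appeared. Aim 2, by contrast, brought subjects back monthly for skin measurements (section VII).

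Two things are at stake. The first is the subject's safety. In week 6, a blister that will heal and one that will progress look alike, and the chance to act early depends on the subject raising it or on staff asking without being told to. The second is the safety record. Minor skin events in the test socket are likely to be under-counted, and a low count could not be told apart from a failure to ask.

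**Working it through.** The plan gives no event rate, sample-size calculation or safety figure to reproduce. The check is mainly one of text, followed by the size of the task.

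**1. Possible capture routes between the adjustment visits and Visit 3A**

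| Route | Where | Does it actively seek a skin event? |
|---|---|---|
| Weekly call | VIII, after Visit 2B | Not as written; compliance is its only stated purpose. It would probably bring out a lesion that stops wear. |
| Adjustment visits | VIII.A | Early, as needed, for comfort of fit; no skin check is stated. |
| Limb measurements and image | VIII, Visit 3A | They describe the limb on that day; a healed lesion may leave no trace. |
| Socket Comfort Score | IX.A | No. It asks: "how would you score the comfort of the socket fit of your artificial limb at the moment". |
| PEQ Residual Limb Health scale | IX.A, given at 2B and 3B | Possibly. The recall period is not stated, and the scale gives a score, not a dated event. |
| Adverse event and complaint reporting | XI | It handles an event once known, serious or not; it plans no questioning. |
| Investigator's judgment to stop a subject | XII | Available, but the investigator must first hear of the event. |
| Internal reviewer and DSMB | XIII | They review data and reports that already exist. |

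Only the PEQ scale asks the subject about limb health, and at Week 16 it comes too late for early action. The rest are passive, tied to one day, or directed at something else.

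**2. Number of calls that could carry the question**

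Inputs: 30 subjects at IU (sections V and VIII); 16 weeks of wear (VIII.A). On the visit calendar, Week 4 to Week 16 is 16 − 4 = 12 weeks.

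- 30 × 16 = 480 calls, or 30 × 12 = 360 on the visit calendar.
- Some subjects may already have finished. The rationale for the amendment speaks of a request to "perform Functional analysis on the remaining subject that will be enrolled for limb health analysis". If 20 or 10 subjects remain (assumption): 20 × 16 = 320 or 10 × 16 = 160.
- The figure could also rise. The Visit 2B note covers "any already enrolled subject completed their limb health part", and the text after it has subjects wear the device for 16 weeks. Read literally, finishers might start a second period. If all 30 did so (an extreme assumption): 30 × 32 = 960.

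**3. Staff time**

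Hours = calls × minutes per call ÷ 60, with 1 to 2 minutes per call assumed.

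| Calls | At 1 minute | At 2 minutes |
|---|---|---|
| 160 | 2.7 h | 5.3 h |
| 320 | 5.3 h | 10.7 h |
| 360 | 6 h | 12 h |
| 480 | 8 h | 16 h |
| 960 | 16 h | 32 h |

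**The case against.** A reader might infer that skin events have no capture route at all. The documents do not support that. Section XI names complaints and untoward events as well as adverse events, and does not limit them to serious ones. A sore mentioned on any call would fall under it. The PEQ scale is a further planned measure, and without its recall period one cannot say that it misses healed events. The call script and the consent pages are not available here, so staff may ask, or subjects may be told to report skin problems. This stands, and it limits the point to the absence of planned active questioning and event-level recording.

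A reader might also infer that section XII overlooks skin events because none of its three listed reasons names them. That does not follow: the list is worded as inclusive, and the sentences before it give the investigator general medical discretion.

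Nor should the gap be read as an established path to ulceration and surgery. A lesion that heals unaided did not take that path, and one that stops wear would probably come up on a compliance call. What remains is the lesion that is still developing while the subject keeps wearing the socket, and whose outcome is unknown at the time.

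Finally, the device is a commercially sold Class 1 product, with quarterly internal review and a DSMB. This lowers the urgency. It does not supply the missing question.

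**Conclusion.** The point holds in a limited form. For about 30 IU subjects, the plan schedules no active skin question and no event-level record between the early adjustment visits and Visit 3A. Capture rests on the subject volunteering the event, with an uncertain contribution from an end-of-study PEQ score. The likely effect is under-recording of minor or developing skin lesions and later notice to the investigator. No planned CHAMP or limb-health model depends on this count.

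The number of missed events cannot be derived from the documents. The figure of 30 is itself probable rather than certain: section V gives OWW separate approval, but the rationale in section VIII mentions the IU and OWW subjects together beside the IU protocol. The 480 calls are a working figure and not a proven maximum. Confidence is moderate, because the call script, the consent text and the PEQ recall period are not available. The sponsor should make the change because it is cheap, not because the trial's conclusions are at risk.

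**What to change.** On each remaining weekly call, add two fixed yes/no items:

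1. Any new blister, sore, ulcer, rash or infection of the residual limb since the last call.
2. Any day on which the socket was not worn, and why.

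Record lesions already present on the date that socket use starts, so that later reports can be called new. Refer each skin yes to the investigator for the judgment that section XII already allows. Give the DSMB a descriptive single-arm count with the number of subject-weeks covered by the questions. Do not attribute events to the device or compare them with the usual prosthesis: there is no matching count during its use, and section X treats these discomforts as common with any prosthesis.

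**Cost.** A short script and form; roughly 8 to 16 staff-hours for 480 calls, less if few subjects remain and more if finishers re-enter; and investigator time for each positive answer. Section XIII requires IRB approval before the change takes effect, and section VIII notes that little study time remained. No visits, subjects or staff are added. The test socket will show a higher, less favourable skin-event count with no comparator beside it, and the report should say so.
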